8.1. Primary Objective

The primary objective is to describe and compare the overall prevalence of MCM among individuals treated with tirzepatide for weight management during pregnancy relative to each of the two comparator cohorts of pregnant individuals (AOM active comparator cohort and AOM unexposed comparator cohort).

8.2. Secondary Objective

The secondary objective is to describe and compare the prevalence of maternal pregnancy complications, fetal and infant outcomes other than MCM, and postnatal growth and development outcomes between pregnant individuals treated with tirzepatide for weight management during pregnancy and the two comparator cohorts of pregnant individuals (AOM active comparator cohort and AOM unexposed comparator cohort). The secondary outcomes of interest are as follows:

Maternal pregnancy complications

- Gestational diabetes
- Pregnancy-induced hypertension
- Pre-eclampsia
- Eclampsia

Fetal outcomes

- Spontaneous abortion (SAB)
- Induced abortion
- Stillbirth

Infant outcomes

- Overall minor congenital malformations
- Preterm birth
- Small for gestational age (SGA)

Postnatal growth and development outcomes

- Postnatal growth deficiency (up to one year of age)
- Infant developmental delay (up to one year of age)

8.3. Exploratory Objective

The exploratory objective is to describe and compare the prevalence of additional maternal, fetal, and infant outcomes of interest between pregnant individuals treated with tirzepatide for weight management during pregnancy and the two comparator cohorts of pregnant individuals (AOM active comparator cohort and AOM unexposed comparator cohort). The exploratory outcomes of interest are as follows:

Maternal pregnancy complications

- Hyperemesis gravidarum (HG)
- Inadequate gestational weight gain (GWG)
- Maternal cardiac disease (e.g., heart failure, cardiomyopathies)

Infant outcome

- Large for gestational age (LGA)
- Rapid infant weight gain (up to one year of age)

9. Research Methods

9.1. Study Design

The Tirzepatide Pregnancy Registry study is a multi-country, prospective, observational cohort study designed to evaluate the association between tirzepatide exposure during pregnancy and subsequent maternal, fetal, and infant outcomes. The registry will enroll participants in the US, the United Kingdom (UK), and Germany. Registry enrollment will be monitored and further expansion to include additional countries will be considered as needed. Participation in the registry is voluntary, and participants can withdraw their consent to participate at any time. Data will be collected from enrolled pregnant individuals and the HCPs involved in their care or the care of their infants, if applicable. The registry is strictly observational; the schedule of office visits and all treatment regimens will be determined by HCPs. No additional laboratory tests or HCP assessments will be required as part of this registry. The design of this pregnancy registry follows current FDA guidance for designing and implementing pregnancy exposure registries.⁴⁵

9.2. Primary Outcome

The primary outcome for the study is MCMs.

9.3. Secondary Outcomes

The secondary outcomes for the study include the following:

- Gestational diabetes
- Pregnancy-induced hypertension
- Pre-eclampsia
- Eclampsia
- SAB
- Induced abortion
- Stillbirth
- Preterm birth
- SGA
- Minor congenital malformations
- Postnatal growth deficiency
- Infant developmental delay

9.4. Exploratory Outcomes

The exploratory outcomes for the study include the following:

- HG
- Inadequate GWG
- Maternal cardiac disease (e.g., heart failure, cardiomyopathies)
- Large for gestational age (LGA)
- Rapid infant weight gain (up to 1 year of age)

The definitions and ascertainment of these outcomes are provided in Section 9.7.3.

9.5. Setting

9.5.1. Study Population

After appropriate alignment with a regulatory authority (e.g., FDA) and institutional review board (IRB)/independent ethics committee (IEC) approval of the protocol, enrollment of individuals in the registry will begin. The registry will enroll patients for up to 10 years, and the enrollment period may be extended if the target sample size is not met, and shortened if the target is met ahead of schedule.

For each enrolled pregnant individual, participation will begin at the time of providing informed consent and end either at pregnancy outcome (if fetal loss – SAB, stillbirth, or induced abortion) or 12 months after pregnancy outcome (if live birth). For each live born infant of prospectively enrolled participants, infant follow-up will begin at birth and end at 12 months of age. For each live born infant of retrospectively enrolled participants, infant follow-up will begin at the time of enrollment and end at 12 months of age; data will be collected retrospectively from time of enrollment to birth outcome. Maternal and fetal outcomes will be assessed through the end of pregnancy, and infant outcomes will be assessed through 12 months of infant age. However, pregnancy outcomes prior to first contact with the Virtual Registry Coordination Center (VRCC) (i.e., retrospectively enrolled participants) will be excluded in the main analysis (Section 9.5.2).

The study population will include three cohorts of pregnant individuals:

- Tirzepatide exposed cohort: A cohort of individuals who are treated with tirzepatide for weight management during pregnancy.
- Anti-obesity medication (AOM) active comparator cohort: A cohort of individuals who are treated with pharmacotherapy other than tirzepatide or other therapies with GLP-1 RA activity for weight management during pregnancy. The comparator AOMs may include, but not limited to, orlistat, setmelanotide, and naltrexone-bupropion.
- AOM unexposed comparator cohort: A cohort of individuals who have obesity or are overweight in the presence of at least one weight-related comorbid condition at the time of conception; and who are not treated with tirzepatide, GLP-1 RA therapies, or any products for weight management during pregnancy.

9.5.2. Inclusion and Exclusion Criteria

For an eligible participant, all inclusion criteria must be answered ‘yes’, and all exclusion criteria must be answered ‘no’. Table 9.1 summarizes the inclusion and exclusion criteria for the cohorts.

[figure not shown]
Table 9.1. Study Population

Cohort	Inclusion Criteria ^a	Exclusion Criteria ^a
Tirzepatide exposed cohort: A cohort of individuals who are treated with tirzepatide for weight management during pregnancy ^{b,c,d}	
 Signed consent obtained before any study-related activities AFAB 15-≤50 years of age at the time of signing consent Currently or recently (within 12 months) pregnant Resident of country included in the study Authorization for their HCP(s) to provide data to the registry Exposure to at least one dose of tirzepatide for weight management at any time during pregnancy^{b,c} Prescribed the qualifying AOM for treatment of obesity^e or overweight with at least one weight-related comorbid condition^f 	
 None^{c,d}
AOM active comparator cohort: A cohort of individuals who are treated with pharmacotherapy other than tirzepatide or other therapies with GLP-1 RA activity for weight management during pregnancy. ^b The comparator AOMs may include, but are not limited to, orlistat, setmelanotide, and naltrexone-bupropion	
 Signed consent obtained before any study-related activities AFAB 15-≤50 years of age at the time of signing consent Currently or recently (within 12 months) pregnant Resident of country included in the study Authorization for their HCP(s) to provide data to the registry Exposure to at least one dose of AOM other than tirzepatide or other therapies with GLP-1 RA activity at any time during pregnancy^d Prescribed the qualifying AOM for treatment of obesity^e or overweight with at least one weight-related comorbid condition^f 	
 Exposure to tirzepatide or other therapies with GLP-1 RA activity at any time during pregnancy^b
AOM unexposed comparator cohort: A cohort of individuals who have obesity or are overweight with at least one weight-related comorbid condition at the time of conception and who are not treated with tirzepatide, GLP-1 RA therapies, or any other approved products for weight management, during pregnancy ^b	
 Signed consent obtained before any study-related activities AFAB 15-≤50 years of age at the time of signing consent Currently or recently (within 12 months) pregnant Resident of country included in the study Authorization for their HCP(s) to provide data to the registry Have obesity^f or overweight with at least one weight-related comorbid condition^g at time of conception 	
 Exposure to tirzepatide or other therapies with GLP-1 RA activity at any time during pregnancy^b Exposure to any other pharmacotherapies for weight management^e at any time during pregnancy^b

Abbreviations: AFAB = assigned female at birth; AOM = anti-obesity medication; BMI = body mass index; DOC = date of conception; GLP-1 RA = glucagon-like peptide-1 receptor agonist; HCP = healthcare provider; LMP = last menstrual period; VRCC = virtual registry coordination center

- ^a Text italicized to highlight differences between cohorts.
- ^b Participants will be considered exposed to tirzepatide or other therapies with GLP-1 RA activity or other products during pregnancy if a dose is taken up to 5 half-lives prior to the DOC (LMP + 14 days). Participants who are exposed to tirzepatide or other therapies with GLP-1 RA activity before pregnancy, but more than the 5 half-lives prior to DOC may be eligible for enrollment into the comparator cohort, if they fulfil certain eligibility criteria.
- ^c Individuals prescribed tirzepatide for reasons other than weight management can be enrolled into the current study, but they are not the focus of the current protocol and will be excluded from the main analysis population (see Section 9.11.1.2).
- ^d In some countries, only patients prescribed tirzepatide according to the approved indications may be included, in accordance with local regulations.
- ^e Eligible comparator medications at this time include orlistat, setmelanotide, and naltrexone-bupropion. Newly approved medications will be reviewed regularly and added if applicable.
- ^f Obesity defined as: BMI ≥ 30 kg/m²
- ^g Overweight defined as BMI ≥ 27 kg/m² and at least one weight-related comorbid condition (e.g., hypertension, dyslipidemia, type 2 diabetes mellitus, obstructive sleep apnea, or cardiovascular disease).

The study aims for inclusive enrollment by incorporating only inclusion criteria common for observational studies, with minimal exclusion criteria. To address potential biases and confounding, the main analysis population for the study will be further limited to individuals who are prospectively enrolled (prior to pregnancy outcome), not exposed to known teratogens and/or investigational medications during pregnancy, not exposed to other GLP-1 RA therapies during pregnancy or within 5-times the half-life of the drug prior to conception, not lost to follow-up, and not already included in the analysis population for a prior pregnancy. The definitions of the main analysis population and the rationale are provided in Section 9.11.1.1.

^a Time to product elimination (5 times terminal half-life); tirzepatide half-life = 5 days; therefore, time to elimination = 25 days

^b If a participant is exposed to the product during this period, they will be considered exposed during pregnancy

^c Participants may be retrospectively enrolled into the registry up to one year after pregnancy outcome but will not be included in main analysis

Figure 9.1. Study flow chart.

9.6. Data Collection

Enrolled pregnant individuals and the HCPs involved in their care or the care of their infants, if applicable, will serve as data reporters to the registry. It is anticipated that most obstetric data will be provided by the individual's obstetric HCP, defined as any HCP who provides care during pregnancy (e.g., obstetrician, family practitioner, general practitioner, midwife), and that the majority of pediatric data will be provided by the infant's pediatric HCP, defined as any HCP who provides pediatric care (e.g., pediatrician, family practitioner, general practitioner). PPD may also request data from other HCPs involved in the individual's or infant's care (e.g., prescriber, specialist, midwife) after appropriate medical release is obtained from the individual.

The data collection process for each participant will begin at enrollment, and cumulative data throughout the pregnancy will be collected at three time points: enrollment, end of the second trimester (approximately 26 gestational weeks), and pregnancy outcome (live birth or fetal loss). For live-born infants, data from pediatric visits will be collected at two time points: 4 months and 12 months after delivery (Figure 9.1). Data collection efforts will be identical for all enrolled pregnant individuals and their infants regardless of their exposures and study cohort assignment.

At enrollment, once consent, registration information (including eligibility criteria), reporter contact information, and medical releases have been provided by the pregnant individual, maternal demographic characteristics, pre-pregnancy anthropometrics, maternal obstetrical history, and family history of congenital malformations will be collected. These data will be collected on the ***Registration Form for Participants***. Registration information, including eligibility criteria, will be confirmed by HCP(s), as appropriate. The HCP(s) will additionally provide maternal pre-pregnancy anthropometrics, maternal obstetrical history, family history of congenital malformations, disease information, pregnancy information, and maternal exposures during pregnancy. All of these data will be collected on the ***Registration Form for Healthcare Providers*** and ***Pregnancy Information Form***. At approximately the end of the second trimester, the HCP(s) will be asked to complete another ***Pregnancy Information Form***, which will collect any updates to pregnancy information and maternal exposures during pregnancy. Around or after the estimated date of delivery (EDD) or after a known pregnancy outcome, the HCP(s) will be asked to complete another ***Pregnancy Information Form*** as well as the ***Pregnancy Outcome Form***, which will collect pregnancy outcome information. For each live-born infant, the pediatric HCP will be asked to complete an ***Infant Outcomes Form***, which will collect infant information, including infant growth and development data, at two time points: at approximately 4 and 12 months after delivery. These visits align with the recommended infant well-child visit (health visitor check) schedules in the study countries.^{45,46}

If a congenital malformation (major or minor) or other event of interest is reported, additional information may be requested from the reporting HCP on the ***Targeted Follow-up Form*** to properly characterize the event. The date each data collection form is completed will also be collected.

Table 9.2 provides a summary of the data collection process, including the forms that will be used to collect the data, the timing for completion of each form, the potential reporters or sources

of the data, and the types of data that will be collected. Section 9.6 provides additional details regarding the data collected. Various approaches may be considered to reduce both healthcare practitioner and participant burden around data collection, and may include use of smart phone applications or other technologies, as appropriate.

Table 9.2. Summary of Data Collection Process

Data Collection Form	Data Sources/Reporters ^a	Timing of Completion	Data Collected ^b
Registration Form for Participants	Participant	Enrollment	Registration information, including eligibility criteria Maternal demographic characteristics Maternal pre-pregnancy anthropometrics Maternal obstetrical history Family history of congenital malformations
Registration Form for HCPs	Obstetric HCP and prescribing HCP, if needed	Enrollment	Registration information, including eligibility criteria Maternal pre-pregnancy anthropometrics Maternal obstetrical history Family history of congenital malformations Disease information Baseline pregnancy information
Pregnancy Information Form	Obstetric HCP and prescribing HCP, if needed	Enrollment, end of second trimester ^c , and EDD/pregnancy outcome ^c	Ongoing pregnancy information Maternal exposures during pregnancy
Pregnancy Outcome Form	Obstetric HCP and pediatric HCP, if needed	EDD/pregnancy outcome	Pregnancy outcome information
Infant Outcomes Form	Pediatric HCP	4 and 12 months after delivery	Infant outcome information at 4 and 12 months
Targeted Follow-up Form	Obstetric, pediatric, or other HCP	Any time after pregnancy outcome	Targeted follow-up information

Abbreviations: EDD = estimated date of delivery; HCP = healthcare provider

^a The primary data source is determined by a hierarchy that is variable specific (e.g., prescribing provider would be primary for disease and exposure information and the obstetric HCP would be primary for pregnancy information). Patients may provide information freely at any point and be considered an initial reporter.

However, these data would not be used in the analysis unless or until the HCP confirms and provides additional follow-up as needed.

^b Data collected at each study site will abide by regulatory guidelines, local privacy laws, and national provisions (e.g., date of birth and race/ethnicity will not be collected from participants in Germany). The collection of race and ethnicity data in the US will comply to the FDA guidance for industry, Collection of Race and Ethnicity Data in Clinical Trials and Clinical Studies for FDA-Regulated Medical Products.⁴⁷

^c Obtain updated information since the previous contact.

9.6.1. Attempts to Obtain Follow-up Information

In the month that the follow-up is due, the HCP will be contacted by PPD and asked to provide follow-up information. If needed, three subsequent attempts will be made approximately every 2 weeks via various modes of communication. If no response is received from the HCP, additional attempts may occur at the next planned data collection time point (e.g., at pregnancy

outcome). When appropriate, the participant will be asked to encourage their HCP to provide the missing data. A final communication to obtain follow-up data will take place indicating that the participant will be considered lost to follow-up if no further data are received. If at any point in the follow-up process the participant withdraws consent or the HCP indicates that the participant is lost to follow-up, no further attempts will be made. The reason the participant was lost to follow-up (e.g., no response from HCP, no response from participant, or participant withdrawal of consent) will be documented.

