9.6.3.2. Retention Strategy

A retention strategy, facilitated by engaging both the participant and HCP, will seek to minimize the reporting burden on these groups to the extent possible.

The registry staff will serve as the first and single point of communication for both registry participants and HCPs. The specialized staff, many of whom are obstetric nurses, have experience collecting data for observational studies from both patients and research naïve HCPs. They are experts at developing a rapport with HCPs and participants to facilitate data collection and build one-on-one relationships that will promote retention and reduce overall loss to follow up. To promote HCP engagement, status updates may be shared with HCPs through various means (i.e., email, newsletters, and the registry website). Materials provided will emphasize the mission of the registry to promote participant engagement and point participants to the website.

The registry will use streamlined data collection processes and simple, concise data collection forms that focus on specified outcomes to reduce the burden of reporting. The registry will provide multiple options for communication and data submission (e.g., phone, fax, mail, email,

website, web based/mobile application) and a flexible follow-up schedule to enhance retention and maximize data reporting. The registry will also attempt to collect contact information of family members or friends in case the participant cannot be reached, which can further promote retention. Finally, in countries where local guidelines permit, the registry will provide stipends to participants (at enrollment and at the end of data collection) and their HCPs who serve as data reporters (once all data have been collected and all queries have been resolved).

Assessment of Recruitment and Retention

Participant recruitment and retention are the greatest challenges experienced with pregnancy registries. Recruitment largely depends on a strong awareness campaign and product use or uptake in the market. It is important to note that low recruitment/enrollment in pregnancy registries may be due to limited use of the product, especially when the product is new to the market. Pregnancy registries typically enroll only a small fraction of all exposed pregnancies, regardless of awareness strategies employed.

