9.6.4. Participant Registration

Pregnant individuals who are interested in providing data to the registry and participating in the registry may self-enroll through the web-based application or by calling the VRCC. To enroll, each individual will answer a series of screening questions to assess their eligibility, and, if eligible, they will be asked to provide informed consent, their primary contact information, alternate contact information for a family member or friend, contact information for HCPs who are/will be involved in their care or the care of their infant, and medical releases to allow these HCPs to provide data to the registry. To allow for full follow-up on all enrolled pregnant individuals and their infants prior to study end, the last participant will be enrolled on or before 31 December 2033.

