9.11.2.1. Analysis of Primary Outcome

Prevalence of the primary outcome will be calculated according to the conventions described in [Table 9.6](#). In general, prevalence will be calculated by dividing the number of cases with an MCM by the appropriate denominator. Prevalence is preferred over incidence when examining pregnancy outcomes, such as congenital malformations, because incidence cannot be reliably estimated given the complexities in the reproductive process.⁹⁷

For MCM, prevalence in the exposed cohort will be calculated among the subset of individuals who are exposed during the first trimester. For the primary analysis, prevalence will be calculated among live births, and a secondary analysis will be conducted among live births and fetal losses ([Table 9.6](#)).

The unweighted univariate regression will be used to compare the crude (unadjusted) relative risks (RRs) of MCM in the tirzepatide exposed and each of the comparator groups, respectively: tirzepatide exposed vs. AOM active comparator and tirzepatide exposed vs. AOM unexposed comparator.

Adjusted methods will incorporate weights estimated using the inverse probability of treatment weighting (IPTW) method to balance the cohorts regarding observable covariates. A weighted generalized linear model using a binomial family and a log (RR) link with robust sandwich variance estimation or a modified Poisson regression⁹⁸ with robust error variance will be employed to estimate an adjusted RR. As with the unweighted analysis, two sets of comparisons will be conducted separately: tirzepatide vs. AOM active comparator and tirzepatide vs. AOM unexposed comparator.

The adjusted comparison of the overall prevalence of MCM observed in the tirzepatide exposed and the comparator cohorts will be considered the primary analysis. A p-value <0.05 will be considered statistically significant.

Table 9.6. Calculation of Primary Outcome Prevalence

Outcome	Numerator	Denominator
Primary analysis: among live births	Live births with confirmed (by adjudication) MCMs (excluding MCMs not known to be associated with medication exposure ^a) among individuals with pregnancy outcome data and, if applicable, exposure during 1 st trimester	Live births among individuals with pregnancy outcome data and, if applicable, ^b exposure during 1 st trimester

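### Section 9.6.1 ends all follow-up once an unspecified provider calls the participant lost, while other contact routes the registry holds are still untried

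*Protocol*

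**What the plan says.** Protocol Section 9.6.1 sets out the contact sequence. An HCP who does not respond gets three repeat attempts about two weeks apart, possibly more at the next data collection point, and a final communication before the participant is classed as lost. Two events cut this short. One is withdrawal of consent: "If at any point in the follow-up process the participant withdraws consent". The other, in the same sentence and with the same consequence, is that "the HCP indicates that the participant is lost to follow-up, no further attempts will be made".

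The registry holds other routes to the data:

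- Section 9.6.4: at enrollment the participant gives her own contact details, those of a family member or friend, "contact information for HCPs who are/will be involved in their care or the care of their infant", and medical releases for these HCPs.
- Section 9.6.3.2: the registry will "attempt to collect contact information of family members or friends in case the participant cannot be reached".
- Section 9.6: "PPD may also request data from other HCPs involved in the" care of the mother or infant. This is permitted, not required.
- Section 9.6.1: "When appropriate, the participant will be asked to encourage their HCP to provide the missing data".

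Table 9.2 assigns pregnancy data mainly to the obstetric HCP and the 4- and 12-month infant forms to the pediatric HCP. Its footnote a says that patient reports are not analyzed until an HCP confirms them. Table 9.6 defines the primary MCM denominator as "Live births among individuals with pregnancy outcome data", with first-trimester exposure where applicable. Completed infant follow-up is not a condition.

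**The concern.** Withdrawal of consent is the participant's decision and must end contact. An HCP's remark that a patient is lost describes only what that HCP knows. She may still be reachable, and so may other HCPs for whom she signed releases. Stopping at that point discards data the registry has consent and means to collect.

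The stake is ascertainment of the primary outcome. Section 9.13 expects little misclassification of MCMs because most are apparent by 12 months and the registry aims to follow infants that long. A rule that can end infant follow-up on one statement weakens that argument. Section 9.13 also concedes that the impact of losses cannot be assessed with any certainty, and offers only a descriptive comparison of characteristics.

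**Working it through.** **1. The rule set against the rest of the protocol**

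| Event | What follows under Section 9.6.1 |
|---|---|
| HCP silent | Three repeats, possible attempts at the next time point, final communication |
| HCP says the participant is lost | No further attempts |
| Consent withdrawn | No further attempts |

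The second row matches the third, so an uninformative reply ends follow-up sooner than silence. The rule applies at any point and refers to the HCP without saying which one. Because obstetric and pediatric HCPs supply data at different times, a literal reading lets a statement from one stop collection from the other. The permissive provisions in Section 9.6 and Table 9.2 footnote a do not override the stop.

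**2. What happens to an infant lost after birth**

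Section 9.11.1.1.5 treats loss outcome by outcome, keeps data up to the loss, and calls a live-born infant lost if there are no follow-up data after birth. An infant seen at 4 months and then dropped does not meet that definition, and Table 9.6 asks only for pregnancy outcome data. Such an infant appears to stay in the MCM denominator, with no later malformation recorded.

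**3. The plan's own figures**

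Inputs (Section 9.9.1): MCM 3% against 9% (RR 3), two-sided alpha 0.05, power 80%, 1:1.

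Walters approximation: power = Φ{√(2n)·[arcsin√(0.09 − 1/2n) − arcsin√(0.03 + 1/2n)] − 1.96}. At n = 265 this gives 0.801, as planned. Enrollment: 265/(0.9 × 0.9 × 0.9) = 363.5, so 364 per cohort and 3 × 364 = 1,092. The sample size is not in error.

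**4. Women lost before pregnancy outcome (they leave numerator and denominator)**

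The 5% loss in Section 9.9.1 is for missing pregnancy outcome data: 0.05 × 364 ≈ 18 per cohort. Suppose, as an assumption not in the protocol, that MCM cases are lost k times as often as non-cases. With true prevalence p and overall loss L, the loss rate in non-cases is l = L/(pk + 1 − p), and observed prevalence is p(1 − kl)/(1 − L).

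Example, k = 3 and L = 0.05:

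- Tirzepatide: l = 0.05/1.18 = 0.0424; 0.09 × (1 − 0.1271)/0.95 = 8.27%.
- Comparator: l = 0.05/1.06 = 0.0472; 0.03 × (1 − 0.1415)/0.95 = 2.71%.
- RR = 3.05.

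At 5% loss with 265 analyzed per cohort:

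| k | Selective in both cohorts: RR (power) | Selective in tirzepatide cohort only: RR (power) |
|---|---|---|
| 2 | 3.02 (78%) | 2.87 (75%) |
| 3 | 3.05 (77%) | 2.76 (71%) |
| 5 | 3.15 (75%) | 2.58 (62%) |

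Extra loss unrelated to outcome costs only precision. Total exclusions of 15% or 20% instead of 10% leave 364 × 0.9 × 0.9 × 0.85 ≈ 251 or 364 × 0.9 × 0.9 × 0.80 ≈ 236 live births, with power 78% or 75%.

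**5. Infants lost after birth (they stay in the denominator)**

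If a fraction s of MCMs is missed in both cohorts, RR = 0.09(1 − s)/[0.03(1 − s)] = 3, unchanged; only the prevalences fall. If s differs, the RR moves. With an assumed s = 10% in the tirzepatide cohort alone, 8.1%/3% = 2.7. The protocol gives no rate of infant loss, so s cannot be estimated.

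**The case against.** The strongest reply is that the sentence is loosely worded and would not be applied so bluntly. Participants are contacted in practice, since their non-response is a listed reason for loss. Other HCPs may be asked, patients may report at any time, and data up to the loss are kept. Safeguards exist too: Section 9.6 requires identical data collection across cohorts, reasons for loss are documented, abnormal prenatal results in lost participants are summarized, and Section 9.11.2.3 compares lost with analyzed participants within each cohort. All of this stands, and it limits the point. But the alternative routes are optional and none is exempted from the stop, while the safeguards describe losses without recovering data. The example reasons in Section 9.6.1 include none for loss declared by an HCP.

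A reader might infer more than the text supports:

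- **That women referred elsewhere after a complication are dropped.** Section 9.6.1 does not mention transfer, and a patient known to have moved need not count as lost under Section 9.11.1.1.5.
- **That any single provider's word is enough.** The protocol leaves the HCP undefined; it neither says this nor rules it out.
- **That the alternate contact was collected for this case.** Section 9.6.3.2 ties it to a participant who cannot be reached, which is a different situation.
- **That losses will differ by cohort because treated women have more HCPs.** No passage supports this. Active-comparator women are also prescribed drugs, so the argument does not reach Comparison #1; and if one statement ends everything, extra HCPs protect nobody.

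**Conclusion.** The point holds as a poorly fixed operational rule that is cheap to improve. Section 9.6.1 equates an HCP's statement with withdrawal of consent and, followed literally, gives up outcome data the registry could still obtain, including the 12-month malformation data on which Section 9.13 relies.

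It does not show that the primary comparison is biased. How often HCPs will declare loss, how that relates to outcome, and whether it differs by cohort are all unknown. The tables above rest on assumed selectivity. They show that equal selective loss at 5% moves the RR only from 3.0 to between 3.02 and 3.15 and lowers power to 75–78%, while loss selective in the tirzepatide cohort alone would lower the RR to between 2.58 and 2.87.

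It is tempting to take about 8 and 24 expected cases (3% and 9% of 265) and note that one missed case gives 24/7 = 3.4 or 23/8 = 2.9. That shows how few events carry the estimate, but it does not follow from the 5% loss. At the comparator's 3% risk, 18 lost women represent only about 18 × 0.03 ≈ 0.5 of a case, and those women leave the denominator as well.

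**What to change.** In Section 9.6.1:

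1. Let only withdrawal of consent end all attempts at once.
2. Treat an HCP's statement as loss to that HCP only.
3. Before classifying a participant or infant as lost, contact the participant, then the alternate contact, to identify the current HCP and obtain a release; also query the other HCPs for whom releases are held.
4. Record HCP-declared loss or transfer as a separate reason, and tabulate it by cohort.

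The cost is a change of wording and of the contact script, a few extra contacts by existing registry staff using details already collected, and slight added burden for the participants concerned. The sample size need not change.
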